5.4 Hospitalization during study participation and mortality

5.4.1 Documentation

Events (hospitalizations and death of any cause) are recorded continuously in the medical practices. Additionally, health insurance funds will be asked to provide data about hospitalizations. For patients with withdrawal of informed consent no data will be provided by health insurance funds. The different sources and the result of the blinded adjudication by the CEC will be documented.

Apart from hospitalizations and death no further adverse events are collected.

5.4.2 Event classification (according to CEC Charta Version 3.0)

A blinded Clinical Event Committee (CEC) will adjudicate all hospitalizations occurring after randomization according to pre-specified criteria in the CEC Charta:

Hospitalization

For this study, ‘hospitalization’ is defined as a hospital admission (elective or emergency as documented in the electronic case report form (eCRF) resulting in an overnight stay with date change even if total duration is less than 24 hours. It also includes emergency room visits with date change.

Planned hospitalization

Hospitalizations for diagnostic procedures, elective interventions (such as change of a device battery), or rehabilitative measures are considered to be ‘planned hospitalizations’ and will not be counted as a hospitalization event with regards to the primary or secondary variables of this study.

For the avoidance of doubt, for a hospitalization that is considered a ‘planned hospitalization’, the patient must not have had signs or symptoms of worsening cardiovascular diseases.

If in doubt and if data is available, a ‘planned hospitalization’ can be characterized due to a time-gap between indication and admission.

If the health insurance company has to give a confirmation to cover the costs of the planned hospitalization prior admission to the hospital, this information can be cross-checked.

Cardiovascular hospitalization

Cardiovascular hospitalization will be defined as a hospitalization due to cardiovascular disease or development of a cardiovascular condition during a hospitalization that is

considered to have caused a prolonged hospital stay. Cardiovascular diseases include heart failure, angina, myocardial infarction, syncope, arrhythmia (including atrial fibrillation), stroke, transient ischemic attack, acute peripheral vascular emergencies, pulmonary embolism or other cardiovascular conditions.

Hospitalization with worsening heart failure

A cardiovascular hospitalization will be classified as 'with worsening heart failure' if the reason for admission is worsening heart failure or worsening heart failure is one of the major components of the admission. Hospitalization with worsening heart failure includes signs and symptoms of heart failure induced by supraventricular or ventricular arrhythmias, acute coronary syndromes or renal dysfunction due to worsening of cardiac function (cardio-renal syndrome). If arrhythmias are associated with signs or symptoms of heart failure, the hospitalization will be adjudicated as 'hospitalization with worsening heart failure'. The CEC diagnosis will be made using the criteria described below, irrespective of the investigator and/or discharge diagnosis.

The following two criteria must apply to adjudicate 'hospitalization with worsening heart failure':

(1) Presence of two typical heart failure signs or symptoms (including shortness of breath, dyspnoea on exertion, paroxysmal nocturnal dyspnoea, orthopnoea, fatigue, reduced exercise tolerance, pulmonary oedema, jugular vein distensions, pulmonary rales, S3 on cardiac auscultation, hepatojugular reflux, altered hemodynamics, peripheral oedema, and cardiomegaly)

OR:

Objective evidence for worsening heart failure (as revealed by echocardiography, chest radiography, or measurement of a natriuretic peptide)

AND:

(2) Intensification of heart failure therapy (e.g. changes/introduction of intravenous medication (i.e. a vasodilator or an inotropic agent, or a diuretic) or an increase in oral diuretic therapy for heart failure (e.g. an increase of furosemide ≥ 40 mg or equivalent or the addition of a loop diuretic to a thiazide diuretic)).

For the avoidance of doubt, if the patient developed worsening of heart failure during a hospitalization (but heart failure was not the reason or a major component of the respective hospital admission), this will not be judged a 'hospitalization with worsening heart failure' but will be deemed a '(planned) cardiovascular hospitalization', if the respective criteria are fulfilled.

Other hospitalizations

Hospital admissions not related to cardiovascular diseases will be classified as 'other hospitalization' (i.e. non-cardiovascular hospitalization).

5.5 Pharmacy claims data from data processing centres and health insurance funds

All known German data processing centres (Apothekenrechenzentren) will be asked to send pharmacy claims data of prescribed medicinal products dispensed at community pharmacies for PHARM-CHF patients to the cost of any statutory health insurance (SHI) funds for the whole study duration and additionally for the measurement of baseline adherence for the 183 days before randomization. In addition, health insurance funds (SHI and private) will be asked to provide data about reimbursed medicinal products dispensed at community pharmacies for the same period. The prescribed medicinal product together with dispensing date and the source of information will be documented.

For patients with withdrawal of informed consent no pharmacy claims data will be available. Therefore, the PDC for these patients cannot be calculated.

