### 11.5.3 Exclusion Bias

Potential bias:

Patients of the intervention group may stop following the study protocol because they do not want to visit the pharmacy as frequent as required or because they do not like the weekly dosing aids.

→ Intention-to-treat-analysis

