1.2 Sample size considerations

Assuming a baseline PDC for cardiovascular medication of 0.7 and a standard deviation of the PDC of 0.22 a sample size of N=176 (88/group) patients is needed to detect a 10% difference between the intervention group and the usual care group with a power of 85% and an alpha of 5%. Assuming a dropout and lost to follow-up of 30% N=248 patients have to be enrolled in the study. The planning is based on a two-sided t-test and performed by means of SAS Version 9.4.

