2.3 Per-protocol population

The per-protocol (PP) population consists of all subjects of the ITT population who completed the study without major protocol violations – that are violation of inclusion criteria, meeting any exclusion criteria, post-baseline data not available, consolidated medication plan not available (intervention group patients only) and terminated the study prematurely (except death).

The following protocol violations are defined as major and will lead to exclusion from the PP population:

- Terminated the study prematurely (except death) within the first twelve months

This will result in the following sizes of the analysis populations:

Table 3 Major protocol violation and per-protocol population

Population	Intervention group	Control group	Total
Randomized	130	128	258
ITT	110	127	237
- patients excluded: termination within the first twelve months	8	2	10
withdrawal of informed consent	6	1	7
discontinued	2	1	3
PP	102	125	227

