6.1 Missing values

No substitution of missing values will be done.

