The primary analysis population for both adjustment types is the ITT population. However, the primary analysis (both adjustments) will be repeated for the PP population for sensitivity. As a further sensitivity analysis an analysis of (co)variance (AN(C)OVA) for the PDC will be done with PDC as dependent variable, and the further fixed effects treatment (intervention vs. control), data from health insurance funds (yes/no), sex (male vs. female), age (≤ 75 vs. > 75 years), NYHA functional class (I and II vs. III and IV), PHQ-9 score (score < 10 vs. ≥ 10) and diabetes mellitus (yes vs. no). The study region will be omitted since this may lead to an over determination of the analysis model.

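### The primary ITT analysis of PDC is in effect a complete-case analysis of at most 104 v 126 patients, and no planned analysis tests the lopsided loss of consent withdrawers (6 v 1)

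*SAP*

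**What the plan says.** - **Primary population.** SAP 7.8: "The primary analysis population for both adjustment types is the ITT population". SAP 2.2 (Table 2) and SAP 4 fix that population at 110 intervention and 127 control patients.
- **Who is in it.** SAP 2.3 (Table 3) starts from the 237 ITT patients and removes 10 to form the per-protocol (PP) set, under the line "patients excluded: termination within the first twelve months". Of these, 7 withdrew consent (6 v 1) and 3 discontinued for other reasons (2 v 1). All 10 count as ITT.
- **Their outcome.** SAP 5.5: "For patients with withdrawal of informed consent no pharmacy claims data will be available. Therefore, the PDC for these patients cannot be calculated". Protocol 11.3 gives the reason: data of patients who withdraw consent are anonymised at once, so nothing can be obtained from insurers or other sources.
- **Missing data.** SAP 6.1: "No substitution of missing values will be done". SAP Table 4 has rules for death and, in Version 2, for discontinuation. It has none for withdrawal of consent.
- **Sensitivity analyses.** SAP 7.8 lists a repeat in the PP population and an AN(C)OVA adjusted for insurance-fund data and the minimization factors other than region.
- **Bias section.** Protocol 11.5.3 foresees that intervention patients may give up because of the pharmacy visits or the dosing aids, and names as remedy "Intention-to-treat-analysis".

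**The concern.** Taken together, these rules mean that the analysis called ITT cannot include every ITT patient. It is a complete-case analysis, and the SAP neither says so nor defines the evaluable subset.

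The loss is uneven. Only the intervention arm carries the burden of weekly or bi-weekly pharmacy visits, and six of the seven known withdrawals are in that arm. If patients who left the programme also filled fewer prescriptions, leaving them out raises the intervention mean and ranks on the primary endpoint.

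No listed analysis could reveal this. The PP set already excludes the same seven patients, and the adjusted model needs an observed PDC. Agreement between the ITT and PP results would carry almost no information on this point.

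**Working it through.** **Planning figure.** SAP 1.2 states that "a sample size of N=176 (88/group) patients is needed to detect a 10% difference" "with a power of 85% and an alpha of 5"%. It adds: "The planning is based on a two-sided t-test". With a difference of 0.10 and SD 0.22, the noncentral t calculation gives 87.9, so 88 per group and 176 in total. The stated figure is reproduced.

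**Patients who can be analysed (Tables 2 and 3).**
- ITT: 130 − 17 − 3 = 110; 128 − 0 − 1 = 127; total 237.
- ITT less consent withdrawals: 110 − 6 = 104; 127 − 1 = 126; total 230. This is an upper limit, because Table 3 counts only the first twelve months while SAP 5.5 covers any withdrawal.
- PP: 110 − 8 = 102; 127 − 2 = 125; total 227.
- PP against analysable ITT: 230 − 227 = 3 patients, or 3/230 = 1.3%.

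**Imbalance.** 6/110 = 5.5% v 1/127 = 0.8%; Fisher's exact p = 0.052.

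**Power (difference 0.10, SD 0.22, t-test).** 110 v 127: 93.5%. 104 v 126: 92.7%. PP: 92.4%. Power is not the problem.

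**Shift on the mean scale.** Let M be the observed intervention mean in the 104 and x the mean PDC of the six withdrawers. The intervention mean over all 110 falls by (6/110) × (M − x). M = 0.80 is an assumption (planning value 0.70 plus the 0.10 effect).

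| x | Fall in mean, points (M = 0.80) | Difference left if 10 points observed | Difference left if 7 points observed (M = 0.77) |
|---|---|---|---|
| 0.7 | 0.5 | 9.5 | 6.6 |
| 0.5 | 1.6 | 8.4 | 5.5 |
| 0.3 | 2.7 | 7.3 | 4.4 |
| 0 | 4.4 | 5.6 | 2.8 |

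The last two columns set the control withdrawer at the control mean of 0.70. With the six at 0 and the control patient at 1, a 10-point difference becomes 5.4.

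**Threshold for p = 0.05 (SD held at 0.22).** For 104 v 126: 1.96 × 0.22 × √(1/104 + 1/126) = 0.057. For 110 v 127: 1.96 × 0.22 × √(1/110 + 1/127) = 0.056. An observed 10-point effect stays above this unless the six are near zero. An observed 7-point effect falls below it once x reaches about 0.5.

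**Shift on the rank scale.** The first primary test is van Elteren, so means are not enough. An unstratified Wilcoxon rank-sum test was simulated with 104 v 126, control mean 0.70 and SD 0.22. It was then repeated with the six intervention withdrawers ranked lowest and the control withdrawer highest. Chance of significance, good to a point or two:

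| True difference | PDC distribution | Withdrawers omitted | Worst rank |
|---|---|---|---|
| 10 points | normal | 92% | 64% |
| 10 points | Beta | 99% | 92% |
| 8 points | normal | 76% | 39% |
| 8 points | Beta | 92% | 66% |

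The worst-rank figures are bounds, not predictions.

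**The case against.** The loss is 7 of 237 patients (3%), it is declared, and it cannot be recovered. SAP 5.5 states it openly and Table 3 prints it by arm. SAP 7.2 tabulates withdrawal of consent separately from discontinuation, and SAP 7 reports n by treatment group, so a careful reader will find the analysed number. If the planned effect is real and PDC is roughly Beta-distributed, even the worst ranking rarely changes the result. All of this stands. It lowers the priority of the point, but it supplies no analysis of what the loss could do.

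Four stronger readings are tempting, and the documents do not support them.

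- *The ITT remedy of Protocol 11.5.3 fails altogether.* It does not. Claims come from data centres and insurers, not from attendance at the study pharmacy. Table 4 Version 1 follows patients to 365 days, so someone who stops the visits but keeps consent can still have a PDC. The remedy fails only for those who withdraw consent.
- *The sponsor offers the PP repeat as its check on withdrawal.* Neither document says this. SAP 7.8 offers it only for sensitivity in general, so there is nothing to retract. The point is only that it cannot serve as such a check.
- *The result is biased towards the intervention.* No section gives reasons for withdrawal or the adherence of those who withdrew. All were to enter on stable medication, and disliking the visits is not the same as not filling prescriptions. The direction is an inference.
- *6 v 1 is the full extent of missing PDC.* It counts first-year consent withdrawals only. The arm split of any other missing PDC is unknown, so the Fisher p describes early withdrawals and nothing more.

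The 17 intervention patients without a medication review were removed before the ITT set was formed. They are a separate matter.

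**Conclusion.** The point holds, at moderate weight. The SAP's primary PDC test is a complete-case analysis of at most 104 v 126 patients under an ITT label. Its known loss is lopsided, and no listed analysis can show whether the result depends on it.

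The likely effect is small: about 0.5 to 1.6 points on the intervention mean for PDCs of 0.7 to 0.5, against a planned effect of 10 points. It reaches 4.4 points only if all six had no coverage at all. These figures assume an observed intervention mean of 0.80. The conclusion is at risk mainly if the observed effect is nearer 7 or 8 points than 10. The rank-test figures also rest on the assumed PDC distribution and on an unstratified test.

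**What to change.** 1. In SAP 7.8, label the primary set as ITT patients with a calculable PDC, and state the number analysed by arm (at most 104 v 126).
2. Pre-specify one sensitivity series on all 237 ITT patients:
   - a worst-rank van Elteren test, with intervention withdrawers ranked lowest and the control withdrawer highest, presented as a bound;
   - a tipping-point series, for example with the missing intervention PDC set to 0.7, 0.5, 0.3 and 0.
3. State the stratum for withdrawers. The test is stratified by insurance-fund data (yes/no), and SAP 5.4.1 and 5.5 leave these patients with none, so they belong in the stratum without fund data.
4. Handle any other missing PDC in the same way, including that from later withdrawals. Since SAP 6.1 bars substitution, add there that this series is an exception for sensitivity only.

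The PP repeat can stay as it is. The cost is a few sentences, a few extra runs of the same test, and a slightly smaller stated primary N. No new data are needed.

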5.6 Primary efficacy variable

The primary efficacy variable is medication adherence, pre-specified as a significant difference of the proportion of days covered (PDC) between the intervention and control group using pharmacy claims data for three CHF medications [angiotensin-converting enzyme inhibitors or angiotensin receptor blockers (ACEi/ARB), β -blockers (BB), and mineralocorticoid receptor antagonists (MRA)] prescribed at baseline.

Medication adherence will be calculated based on the PDC during the 365-days following randomization. The dose information documented at screening / visit 1 or in case of switches at visit 3 will be used. Medication switches, stockpiling, inpatient days (hospital stays), medication fills prior to randomisation, and death will be considered. To measure baseline adherence, the PDC for the period 183-days before randomization to randomization for each drug class (ACEi/ARB, BB, MRA) will be analysed.

In case of inpatient days, the proportion will be adjusted by excluding days from both the numerator and denominator assuming that patients did not deplete their medication on their medication supply on those excluded days. If a patient switches medications within a class (including ACEi/ARB), the patient's medication supply will be replaced with the new medication supply. If a patient dies, all days following the death will be censored.

Existing medication at randomization (=day 1) and medication dispensed during 14 days after randomization (=day 1) will be considered if at least one additional dispensing occurred during the 365-days follow-up. Existing medication at randomization will be captured, but only the days during the 365-days follow-up will contribute to the final proportion.

Adherence for all three CHF medication classes, if prescribed, will be calculated and can range from 0 to 1.0 (perfect adherence) and will then averaged across all non-missing classes of medications to derive the summary PDC.

PDC:

- PDC at Baseline (183 days), 365 days, 730 days and Individual Follow-up time
- PDC ACEI/ARB at Baseline (183 days), 365 days, 730 days and Individual Follow-up time
- PDC BB at Baseline (183 days), 365 days, 730 days and Individual Follow-up time
- PDC MRA at Baseline (183 days), 365 days, 730 days and Individual Follow-up time
- PDC statins at Baseline (183 days), 365 days, 730 days and Individual Follow-up time
- *Derived: all PDC-values will be categorized as: < 80% and ≥ 80% and < 88% and ≥ 88%*

Table 4 PDC analyses - definition for 365 days' follow-up

	Intervention group (IG) and control group (CG)
ITT	Version 1) From randomization until 365 days following the randomization If a patient dies: the sum of days between randomization and date of death Version 2) If a patient discontinues within 365 days: the sum of days between randomization and discontinuation

5.7 Primary safety variable

The primary safety variable is all-cause mortality or unplanned cardiovascular hospitalizations as days lost due to unplanned cardiovascular hospitalizations or death of any cause between baseline (day of randomization) and 365 days. For death, the remaining days to 365 days will be counted. The days spent in hospital will be added to the days after death until 365 days.

The percentage of days lost due to hospitalisation and death will be calculated as the ratio of the sum of the number of days lost due to death and spent in hospital during the 365-days follow-up and the respective patient follow-up time, expressed in percent.

If a patient terminated the study within 365 days, the days lost between the day of randomization and the day of discontinuation will be analysed accordingly.

For days lost due to unplanned cardiovascular hospitalizations, the admission und discharge day will be counted as one day. Calculations will be done in days.

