## 11.4.2 Primary Safety Analysis

The primary safety variable is all-cause mortality or unplanned cardiovascular hospitalizations as days lost due to unplanned cardiovascular hospitalizations or death.

The number of days lost due to death of any cause or unplanned cardiovascular hospitalizations will be analysed by a Wilcoxon signed-rank test comparing both treatment groups. Additionally, the number of days lost due to death of any cause or unplanned cardiovascular hospitalizations will be analysed descriptively by treatment group and in total.

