5.9 Secondary safety variables

The following secondary safety outcomes will be evaluated during 365-days follow-up according to the primary safety variables:

- Percentage of days lost due to unplanned cardiovascular (CV) hospitalizations or all-cause death
- All-cause mortality or unplanned cardiovascular hospitalizations as recurrent event (number)
- Unplanned cardiovascular hospitalizations (recurrent event, number)
- Unplanned hospitalizations for heart failure (recurrent event, number)
- Days lost due to hospitalizations of any cause or death
- Percentage of days lost due to hospitalizations of any cause or death of any cause
- Unplanned all-cause hospitalizations
- All-cause mortality

The following secondary safety outcomes will be evaluated during the patient's individual time within study (=individual follow-up time):

- All-cause mortality or unplanned cardiovascular hospitalizations as recurrent event (number)
- Unplanned cardiovascular hospitalizations (recurrent event, number)
- Unplanned hospitalizations for heart failure (recurrent event, number)
- Percentage of days lost due to unplanned cardiovascular hospitalizations
- Percentage of days lost due to hospitalizations of any cause
- Unplanned all-cause hospitalizations

- All-cause mortality

Table 5 Secondary safety variables - Definition of patients' individual follow-up time

	Intervention group (IG) and control group (CG)
ITT	From randomization until end of study. End of study: 
 - 31.12.2016 - If date of visit 6 or last visit in 2017: 31.12.2016 - If date of final study visit before 30.06.2016: Date of visit 6 - Death: date of death - Withdrawal of informed consent: date of withdrawal - Premature termination of study: date of premature termination

The percentage of days lost due to hospitalisation will be calculated as the ratio of the sum of the number of days lost due to stays in hospital during the respective patient follow-up time and the respective patient follow-up time, expressed in percent.

For days lost due to unplanned cardiovascular hospitalizations, the admission und discharge day will be counted as one day. Calculations will be done in days.

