7.9 Primary safety analysis

The primary safety variable is all-cause mortality or unplanned cardiovascular hospitalizations as number of days lost due to unplanned cardiovascular hospitalizations or death between baseline (day of randomization) and 365 days.

The percentage of days lost due to death of any cause or unplanned cardiovascular hospitalizations as the fraction of maximum possible days alive and out of hospital will be analysed by a Wilcoxon signed-rank test comparing both treatment groups. Additionally, the number of days lost due to death of any cause or unplanned cardiovascular hospitalizations will be analysed descriptively by treatment group and in total.

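### Individual-follow-up days lost: SAP 7.10.2 counts death, but SAP 5.9 and Table 5 leave death no days; the all-cause percentage also has an unusable denominator

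*SAP*

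**What the plan says.** **Individual follow-up.** For this window SAP 5.9 lists two days-lost percentages, both for hospital stays only. Its formula is the ratio of the "number of days lost due to stays in hospital during the respective patient follow-up time and the respective patient follow-up time". Table 5 of that section sets the end of follow-up for a patient who dies as "Death: date of death". SAP 7.10.2, however, defines a secondary variable over the same window as the percentage of days lost to unplanned cardiovascular hospitalization or death, and relates it to the maximum possible days.

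**365 days.** SAP 5.7 states: "For death, the remaining days to 365 days will be counted". Its percentage is the ratio of the "number of days lost due to death and spent in hospital during the 365-days follow-up and the respective patient follow-up time". Patients who terminate early are analysed up to the day they stop. SAP 5.9 says that its 365-day outcomes follow the primary safety variable, and these include "Percentage of days lost due to hospitalizations of any cause or death of any cause". For the all-cause composite, SAP 7.10.2 instead takes days lost relative to the days actually spent alive and outside hospital.

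**Tested quantity.** Protocol 11.4.2: "The number of days lost due to death of any cause or unplanned cardiovascular hospitalizations will be analysed by a Wilcoxon signed-rank test". SAP 7.9 names the number as the primary safety variable. It then tests the percentage "as the fraction of maximum possible days alive and out of hospital will be analysed by a Wilcoxon signed-rank test comparing both treatment groups" and leaves the number descriptive. SAP 5.9 lists "Percentage of days lost due to unplanned cardiovascular (CV) hospitalizations or all-cause death" as secondary over the same 365 days.

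**The concern.** The main conflict is over death in the individual-follow-up window. SAP 7.10.2 puts death into a variable whose window, under Table 5, closes on the day of death. Two programmers could each follow the SAP and deliver different variables, one containing death and one not. Under the Table 5 reading, a table labelled hospitalization or death would show hospital days only, and an early death would look like a good outcome.

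The all-cause composite has a different problem. A share of time cannot exceed 100%, but the 7.10.2 denominator allows it.

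The number/percentage mismatch in SAP 7.9 concerns the primary safety analysis, so it needs tidying even though its numerical effect is small.

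**Working it through.** The plan gives no effect size or power for days lost, so there is no figure of its own to reproduce. The patients below are invented to show what each rule does. I read the signed-rank test named in the plan as the two-sample rank-sum test, because the arms are independent groups.

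**1. Individual follow-up (SAP 5.9 and Table 5 against 7.10.2).** Let d be the day of death, h the cardiovascular hospital days and H the day follow-up would otherwise have ended. H is assumed here, because no section defines it for a patient who has died.
- Window closed at death: h/d. No days lie after death inside the window, so the composite equals the hospital-only percentage for every patient.
- Death counted to H: (h + H − d)/H.

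| Patient | Closed at death | Counted to H |
|---|---|---|
| d = 30, h = 0, H = 730 | 0/30 = 0% | 700/730 = 95.9% |
| d = 30, h = 0, H = 500 | 0/30 = 0% | 470/500 = 94.0% |
| d = 400, h = 12, H = 730 | 12/400 = 3.0% | (12 + 330)/730 = 46.8% |

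**2. All-cause composite.** SAP 5.9 lists the all-cause percentage with death only for 365 days, so that window is used. Days lost L = h + (365 − d), where h now counts all hospital days. Days alive and outside hospital A = d − h. The maximum possible is 365.

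| Patient | L | L/A | L/365 |
|---|---|---|---|
| d = 100, h = 10 | 275 | 275/90 = 305.6% | 75.3% |
| d = 300, h = 10 | 75 | 75/290 = 25.9% | 20.5% |
| d = 182, h = 0 | 183 | 183/182 = 100.5% | 50.1% |

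Lost days and actual days add up to the maximum. With x = lost/maximum, lost/actual is therefore x/(1 − x). This rises steadily with x and passes 100% at x = 0.5. Patients keep the same order, so a rank test over the same window gives the same p-value and only the reported values change.

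**3. Number against percentage (SAP 7.9 and Protocol 11.4.2).** SAP 2.3, Table 3, gives the ITT patients who terminated within twelve months without dying: 8 of 110 (7.3%) in the intervention group and 2 of 127 (1.6%) in the control group, 10 of 237 in all. For the other 237 − 10 = 227, with 365 as the denominator for completers and deaths, the percentage is the number divided by a constant. A terminator with no hospital day scores zero on both scales, so only a terminator with a hospital day can change rank. For example:
- stopped on day 60 with 15 hospital days: 15 days, 15/60 = 25.0%;
- completed with 30 hospital days: 30 days, 30/365 = 8.2%;
- died on day 300 without a hospital stay: 65 days, 65/365 = 17.8%.

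By number the first patient ranks lowest of the three; by percentage, highest. Simulations used 110 versus 127 patients, 8 versus 2 terminators, assumed one-year mortality of 5–10% versus 10–15%, and 0.4–0.6 versus 0.6–0.7 cardiovascular admissions per year. About 2 patients on average were affected, and significance changed in 0.3–1.5% of runs.

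**The case against.** Much of the opposing case stands, and it rules out several stronger readings.

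- A reader might infer that the primary 365-day denominator is itself contradictory. It is loosely worded, but SAP 5.7 counts days after death to day 365 and has a separate rule for early terminators, and 7.9 refers to the maximum possible. Together these imply 365 for completers and deaths, and days to termination otherwise.
- A reader might infer that the protocol's primary safety quantity goes untested in any meaningful sense. Its formal test is replaced, but the ranks are nearly the same. Listing the percentage as secondary in 5.9 agrees with the protocol; the sentence in 7.9 is the outlier.
- The all-cause denominator could be called a slip, since 5.9 ties the 365-day outcomes to the primary definition. That is fair, but the analysis section still instructs a different calculation.
- A reader might infer that the trial loses its mortality signal. It does not. Over individual follow-up, death also enters the recurrent-event composite (negative binomial model), its time-to-first-event Kaplan-Meier display and the logrank test of mortality.
- A reader might infer a large loss of power. With an assumed mortality hazard ratio of 0.5 and equal admission rates, the closed window rejects in 4.6–6.0% of runs and a death-included version in 15–64%. The first figure follows by construction, because a hospital-only measure has nothing to detect when admissions are equal. At hazard ratio 0.8 and 10% control mortality per year the contrast is 5% against 8–10%; with 25% fewer admissions as well, 25–26% against 27–34%. In the hazard-ratio-0.5 scenarios the logrank test rejected in 38–77%.

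The individual-follow-up conflict is not answered. The reference in 7.10.2 to the maximum possible days suggests a longer window, but nothing defines it.

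**Conclusion.** The point holds, chiefly for one secondary variable. SAP 7.10.2 includes death in the individual-follow-up percentage, while 5.9 and Table 5 exclude it. If Table 5 is applied, every death contributes zero days. The all-cause denominator in 7.10.2 can produce values above 100%; over the same window this affects reporting and not the test. The number/percentage mismatch in 7.9 is minor.

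The definitional findings rest on the documents alone. The percentages come from invented patients, and any power contrast is illustrative and depends strongly on the assumed mortality hazard ratio. Secondary p-values are exploratory (SAP 7.10), and the study is powered for the primary efficacy variable only (Protocol 11.1). The consequence is therefore ambiguous or misleading safety tables, not a threat to the main conclusion.

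**What to change.** 1. **Individual follow-up.** Preferably make 7.10.2 match 5.9: drop death from this percentage and rename it hospital-only, since other analyses in this window already cover death. If death is kept, state one horizon in advance, for example 31.12.2016 for every patient who died, because such a patient may have no visit 6 date. Count the days from death to that date as lost and divide by the time from randomization to that date. Divide non-death terminators by their time to termination.
2. **All-cause composite.** Replace the denominator in 7.10.2 with the maximum possible: 365 for completers and deaths, and days to termination for non-death early terminators. State the same rule in 5.7.
3. **Primary safety test.** Test the number in 7.9, as in Protocol 11.4.2, and keep the percentage as the secondary variable in 5.9.

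The cost is SAP wording and changes to derived variables. No new data are needed.
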